12.2. Sample Size Considerations

For the primary clinical study outcome of OM severity (WHO OTS scale) at end of RT/chemoRT, for simplicity, and for conservative sample size estimation, we consider subjects with grades 0, 1, 2 OM as having a successful outcome, and with OM grade greater than 2 as a failure. Subjects who never develop or scored 1 on the WHO mucositis scale will be considered as a success if they complete the end of treatment visit. The overall study will randomize 120 subjects in four strata. Sixty-five percent of eligible participants are expected to be treated with RT alone, the remaining 35% are expected to be treated with chemoRT. Approximately 45% of participants are expected to receive Proton therapy, 55% IMRT. The expected overall success rate on RT or chemoRT is estimated as 30% with SOC. With 1:1 randomization into the 2 treatment arms, with 80% power and 2-sided alpha of 0.05, we can detect a difference in this success rate of |26.5 %| based on Fisher's exact test for proportions (exact alpha = 0.03; 60 subjects per arm across the four strata). Further, within the RT stratum with 39 subjects/intervention arm, we can detect a difference of |33.3%| and within the chemoRT stratum with 21 subjects/intervention arm, we can detect a difference of |46.7%|. Within the smallest stratum of chemoRT and Proton RT, for example, we would have 9 patients intervention group and a comparable detectable difference of |65%|. While this detectable difference is very large, there is no reason to expect heterogeneity among the strata. However, we will examine the homogeneity of the effects across the four strata using a Gail-Simon test for qualitative interaction. Unless there is a statistically significant difference (at the 0.10 level) in this test for qualitative interaction with respect to outcome and treatment effect in the four strata, results will be combined. Unless otherwise specified, all sample size calculations were performed using PASS 2014 software, NCSS, J. Hintze, Kaysville, UT. Similar sample size considerations would apply to the end of study comparison of OM grade. We note that we evaluate the primary outcome at both the end of RT/chemoRT (Visit 9/FIV), and at the end of study visits (Post-RT Visit). These two time points will be evaluated with no adjustment for multiple analyses.

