12.4. Analysis Plan

Distributions of subject and disease characteristics will be summarized by randomized intervention group (and within strata by intervention group) using descriptive statistics and graphical displays (e.g. boxplots for continuous measurements and frequency displays and contingency tables for ordinal and categorical measurements). These summaries will be provided at baseline and at each study visit, including the end of study visit (Post-RT Visit). Similar descriptive analyses will be provided for all secondary outcomes as well (changes in salivary proinflammatory cytokines, and the following clinical indicators: a) duration of and time to onset of severe OM, b) salivary hypofunction, c) average mouth and throat soreness [MTS], and d) quality of life and function as measured by selected instruments [EORTC QLQ 30 and EORTC QLQ HN35]). The focus will be to identify potential heterogeneity and imbalance of randomization into the study intervention groups.

Primary Objective. The analyses of the primary endpoint will be carried out on the binary OM severity (WHO OTS 0-2, 2-4) at the end of RT/chemoRT and at the end of study using a Cochran Mantel Haenszel test to adjust for strata if there is no evidence of heterogeneity of treatment effect. If there is heterogeneity, results will be examined separately within strata. Individual trajectories of OM severity by visit will be displayed.

Additional analyses of changes over time in OM severity (with ordinal classes) will be examined using mixed effects regression models for subject specific models that require only that data be missing at random [see for example; Applied Longitudinal Data Analysis,³⁵ or General Estimating Equation (GEE) population average models that require data be missing completely at random.³⁶ These approaches take into account repeated observations, missing data, and dropouts and loss to follow up among the subjects.

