Effects of dropouts. Crossovers from intervention to standard of care group and noncompliance. The assumptions of these methods will be evaluated by comparing those subjects who dropout over time with those who do not with respect to baseline, diseases, and treatment characteristics to identify potential differential dropout rates by intervention group, stratification variables, and other factors. Further sensitivity analyses will be conducted to evaluate the effects of dropout rates that may be different between intervention and control group; crossover from intervention to control group; noncompliance on intervention and SOC arms, and missing outcome and covariate data.

Adjustments for covariates. Analyses will incorporate adjustments for baseline variables (e.g. age, gender, cancer diagnosis, tumor location, RT treatment plan and modality, RT dose and targeted sites within the oral cavity) including dental health status and other factors that may impact outcome based on the analyses that compare baseline variables between the two treatment groups. Those variables that are clinically

important or that differ between the two treatment groups at baseline will be considered in these supportive analyses.

Secondary Objectives. Similar methods will be employed for the analyses of the secondary outcomes that include comparisons of changes in cytokine levels over time by treatment intervention and comparisons of changes: a) duration of and time to onset of severe OM, b) xerostomia, & c) average mouth and throat soreness (i.e. other clinical effects of the intervention), quality of life assessments, cytokines, etc.; that are evaluated over time in this study.

WHO Severity compared with CTCAE score. Data will be summarized using contingency tables for these pairwise measurements. The association between the two grading systems will be examined using nonparametric McNemar chi square tests for symmetry.

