Cytokine Analysis. The focus of the analyses of cytokines is to examine the effects of the intervention compared to the control group on OM response that incorporates all the various cytokines measured over time. The strategy for the development of these prediction models for OM response will include logistic regression models (and mixed effect regression models) calibrated with cross validation or penalized logistic regression models such as LASSO,³⁷ and other methods³⁸ to identify salivary cytokines that, individually or jointly, may play a role, in addition to intervention assignment, stratification factors, and patient characteristics, in the development of OM and the severity of OM over time. The distributions of each of the cytokines will be summarized within intervention groups at baseline and over time with summary statistics and graphical displays. Bivariate scatterplots and pairwise correlation coefficients will be estimated. Preliminary analysis will compare the distributions of individual cytokines by treatment group using 2-sample 2-sided t-tests (with suitable transformation of levels if required). With a false discovery rate of 10%, and a power of 80% for each test, we can detect a true difference in cytokine level of at least 0.5 (with estimated within group standard deviations of 1.0). For a single test, the individual test alpha is 0.074; the probability of detecting all 5 tests where the true mean difference in expression > 0.5, is 0.33.

The analysis approaches described above incorporate biomarkers, demographic and clinical predictors (and potential interactions) may increase both sensitivity and specificity in OM prediction or classification accuracy. The resulting models will be evaluated using Receiver Operating Characteristic (ROC) curves and estimating increases in AUC or other appropriate statistical measures of improvement in classification. An optimal cut-off value can be selected using cross-validation by optimizing the Youden index of the ROC analysis.³⁸ Sample size determination for diagnostic accuracy studies involving binormal ROC curve indices. Additional approaches to the development of prediction models will also be considered. Results would require validation in an independent study.

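### The WHO–CTCAE comparison is stated as a question of association, but the only analysis named is a symmetry test, which measures neither association nor agreement

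*SAP*

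**What the plan says.** SAP Section 12.4 (Analysis Plan) has a short paragraph on WHO severity against the CTCAE score. It plans a descriptive display: "Data will be summarized using contingency tables for these pairwise measurements". It then names one inferential method: "The association between the two grading systems will be examined using nonparametric McNemar chi square tests for symmetry".

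No kappa, weighted kappa, percent agreement or rank correlation is named for the two scales there or elsewhere in the SAP. The only correlation coefficients in the plan ("Bivariate scatterplots and pairwise correlation coefficients will be estimated") belong to the cytokine analysis.

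The paragraph does not say in which form the grades are compared, and Section 12.4 uses mucositis severity in two forms. The primary analysis is "carried out on the binary OM severity (WHO OTS 0-2, 2-4"). That label lists grade 2 on both sides; Section 12.2 places it with success: "we consider subjects with grades 0, 1, 2 OM as having a successful outcome, and with OM grade greater than 2 as a failure". The longitudinal analyses keep the grades: "Additional analyses of changes over time in OM severity (with ordinal classes) will be examined using mixed effects regression models".

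**The concern.** Symmetry and association are different properties of a paired table. McNemar's test, and Bowker's extension to more than two categories, compares each off-diagonal cell with its mirror cell. The diagonal, where the scales agree, does not enter.

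- Non-rejection cannot support agreement. Any symmetric table with at least one discordant pair gives a statistic of 0, whether the scales agree closely, moderately or not at all.
- Rejection shows that disagreement is asymmetric. That is compatible with strong association.

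The form of the grades changes what the test means. In a 2x2 table it detects one scale grading above or below the other at the chosen cut. In a larger ordinal table Bowker's test responds to any asymmetry, including one with no net shift.

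At stake is the reading of one supportive result. A large p-value could be reported as showing that the scales agree, and a small one as showing that they are, or are not, related. The test supports none of these conclusions.

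**Working it through.** The SAP gives no figure for this comparison, so there is none to reproduce. The check asks whether the named test can distinguish different strengths of agreement.

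**Inputs.** The number of pairs is 120, one per participant, from Section 12.2 ("The overall study will randomize 120 subjects in four strata"). All cell counts are assumed for illustration and are not trial data.

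**Formulas.** For a 2x2 table [[a,b],[c,d]] with n pairs:
- McNemar (uncorrected) = (b−c)²/(b+c), on 1 df.
- Observed agreement po = (a+d)/n. Chance agreement pe = sum of products of matching margins / n². Kappa = (po−pe)/(1−pe).
- Large-sample SE of kappa = √[po(1−po)/n]/(1−pe).
- Bowker = sum of (n_ij−n_ji)²/(n_ij+n_ji) over mirror pairs.

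**Step 1: different agreement, same test result.**
- [[42,18],[18,42]]: po = 84/120 = 0.70, pe = 0.50, kappa = 0.20/0.50 = 0.40. SE = √(0.21/120)/0.50 = 0.084, 95% CI 0.24 to 0.56. McNemar = (18−18)²/36 = 0, p=1.00.
- [[54,6],[6,54]]: po = 108/120 = 0.90, pe = 0.50, kappa = 0.40/0.50 = 0.80. SE = √(0.09/120)/0.50 = 0.055, 95% CI 0.69 to 0.91. McNemar = (6−6)²/12 = 0, p=1.00.
- At the extremes, [[30,30],[30,30]] (kappa 0) and [[0,60],[60,0]] (kappa −1) also give 0 and p=1.00.

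**Step 2: same agreement, different test result.**
- [[54,10],[2,54]]: po = 0.90, pe = (64×56+56×64)/14,400 = 0.498, kappa = 0.402/0.502 = 0.80, 95% CI 0.69 to 0.91. McNemar = (10−2)²/12 = 5.33, p=0.021 (continuity-corrected 0.043, exact binomial 0.039).

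**Step 3: ordinal grades, asymmetry without net shift.**
- [[20,20,0],[0,40,0],[0,20,20]]: 20 pairs lie one grade above the diagonal and 20 one grade below, so the mean grade difference is 0.
- Quadratic-weighted kappa: the observed mean squared difference is 40/120 = 0.333. The value expected from the margins (40/40/40 and 20/80/20) is 2/3 + 1/3 = 1. Kappa = 1 − 0.333 = 0.67 (bootstrap 95% CI 0.56 to 0.75). Spearman is 0.71 (0.63 to 0.78).
- Bowker = (20−0)²/20 + (0−20)²/20 = 40. On 3 df p=1.1e-8. If the empty mirror pair is dropped, on 2 df, p=2.1e-9.

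**Step 4: how often the test rejects at 5% (2x2, 120 pairs, exact enumeration, uncorrected test).**

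| Discordance | Split of discordant pairs | Rejection probability |
|---|---|---|
| 10% (kappa 0.80 with 50% margins) | 5:5 | 4.4% |
| 20% (kappa 0.60) | 5:5 | 5.3% |
| 30% (kappa 0.40) | 5:5 | 5.0% |
| 10% | 8:2 | 55% |
| 10% | 9:1 | 85% |

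With evenly split disagreement, the rejection rate stays near 5% whether agreement is close or moderate. At a fixed 10% discordance it moves from 4.4% to 85% with the direction of disagreement alone.

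**The case against.** The strongest reply is that the point rests on one word. The paragraph compares paired grades, and a natural question is whether one scale grades systematically higher. McNemar's test suits that question in a 2x2 table, and the SAP itself calls it a test for symmetry. On that reading the fault is a loose use of the word association. The contingency tables are planned, so kappa or a rank correlation could be computed from them at any time, and no treatment comparison depends on the result.

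Part of this stands. The test is valid for symmetry and worth keeping, no information is lost, and the effect on the trial is small. But the stated aim is association, and the one method named does not address it. Planned tables do not supply the missing estimate, and a measure chosen after the tables are seen loses the benefit of prespecification.

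Three technical cautions are also fair, and none changes the conclusion. With perfect agreement the statistic is 0/0, so the statement about symmetric tables needs at least one discordant pair. The degrees of freedom in the ordinal example depend on how an empty mirror pair is treated. And rejection in that example is not a false alarm: the two scales do use the grades differently (margins 40/40/40 against 20/80/20). The example shows that Bowker's test detects asymmetry other than net over- or under-grading, alongside substantial association.

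The unstated choice between binary and ordinal grades would, alone, be missing detail. It matters here because it decides what the named test means.

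**Conclusion.** The concern holds. The SAP announces an examination of association and names only a test of symmetry, with no estimate of association or agreement. In the illustrations, p=1.00 occurs with kappa of −1, 0, 0.40 and 0.80, and kappa of 0.80 occurs with p=1.00 and with p=0.021. The result does not depend on the trial's data; it is a property of the test. The illustrations assume their cell counts and one independent pair per participant.

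The importance is limited. This is a supportive comparison of scales, and the primary endpoint, power and interim boundaries are unaffected. It should be corrected because the analysis as written cannot answer its own question and the correction is nearly free.

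**What to change.** In the WHO–CTCAE paragraph of SAP Section 12.4:

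1. Add one estimate with a 95% confidence interval from the planned tables: a rank correlation, or weighted kappa if a given grade is taken to mean the same on both scales. If visits are pooled, obtain the interval by resampling patients.
2. State whether binary or ordinal grades are compared.
3. Keep the symmetry test and describe it as such: directional over- or under-grading for a 2x2 table, any asymmetry for Bowker's test on a larger table. Do not call it a test of association.

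The cost is one or two sentences and trivial programming. No new data are needed.

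### The preliminary cytokine t-tests carry a 10% false discovery rate with no rule that delivers it, and omit baseline level and strata (low severity)

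*SAP*

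**What the plan says.** The Cytokine Analysis part of SAP Section 12.4 states: "Preliminary analysis will compare the distributions of individual cytokines by treatment group using 2-sample 2-sided t-tests", and allows the levels to be transformed first. A power statement follows. Its premise is "With a false discovery rate of 10%, and a power of 80% for each test", and its target is a difference of 0.5 against an SD of 1.0 in each arm. On the level of each comparison it says: "For a single test, the individual test alpha is 0.074". It puts the chance of finding all five true differences at 0.33.

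The SAP does not give the number of cytokines tested, the visit or visits tested, or the procedure that turns observed p-values into declarations at 10% FDR. The t-tests as described have no baseline or stratum term.

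Two other statements bear on this. Baseline levels are available: "The distributions of each of the cytokines will be summarized within intervention groups at baseline and over time". The Secondary Objectives paragraph of Section 12.4 separately plans "comparisons of changes in cytokine levels over time by treatment intervention", by methods similar to those for the primary outcome.

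**The concern.** An FDR is a property of a decision rule applied to a set of p-values. The SAP states the rate but not the rule, and 0.074 is the only per-test level it offers. That level depends on how many cytokines truly differ, which is what the tests are meant to find out. An analyst who took it as the threshold would report cytokines under a 10% label that holds only if about as many differ as planned.

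The t-tests are also the only cytokine comparison with any stated error control. They ignore each patient's own baseline level and the four randomisation strata. The primary test in the same section is adjusted for strata when treatment effects are homogeneous. Omitting a baseline value that predicts follow-up gives up precision at no saving in data.

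**Working it through.** **Inputs from the SAP.** FDR f = 0.10, power 0.80 per test, difference 0.5, SD 1.0, per-test alpha 0.074 two-sided and 5 true differences (Section 12.4); 60 per arm (Section 12.2). The number of tests is not stated.

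**1. Reproducing the plan's figures.** The FDR planning formula with m1 true effects and m0 nulls is

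alpha = m1 × power × f / [m0 × (1 − f)].

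With m1 = 5, solving for m0 gives 6: 5 × 0.8 × 0.1 / (6 × 0.9) = 0.0741. With 5 nulls it would be 0.0889 and with 7 nulls 0.0635. The chance of detecting all five is 0.8^5 = 0.328, the stated 0.33. At 60 per arm, difference 0.5, SD 1 and alpha 0.074, the two-sample t-test has power 0.825. All stated figures are therefore consistent. The 11 tests (5 + 6) are inferred, not quoted, and are an assumption below.

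**2. What 0.074 would do as a fixed cut-off.** Assume 11 independent tests and 80% power. Let V be the false and S the true declarations, with V ~ Bin(m0, 0.074) and S ~ Bin(m1, 0.80). The FDR is the mean of V/(V + S), taken as 0 when nothing is declared. The planning ratio is m0 × 0.074 / (m0 × 0.074 + m1 × 0.80).

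| True effects of 11 | Planning ratio | Exact FDR |
|---|---|---|
| 5 | 10.0% | 8.7% |
| 4 | 13.9% | 11.8% |
| 3 | 19.8% | 16.3% |
| 2 | 29.4% | 23.1% |
| 1 | 48.1% | 34.6% |

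For example, with 2 true: 9 × 0.074 = 0.666, and 0.666 / (0.666 + 1.6) = 0.294.

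Sensitivity of the exact FDR:
- 5 true with 4, 6, 7 or 8 nulls: 5.9%, 8.7%, 10.0%, 11.3%. With few nulls the cut-off is conservative.
- 3 true with 8, 15 or 20 tests in all: 11%, 23%, 30%.
- Correlation 0.5 between 11 cytokines (simulated), 5 down to 1 true: 9%, 12%, 15%, 20%, 27%.

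**3. Benjamini-Hochberg at q = 0.10.** Simulation with 100,000 runs, difference 0.5 SD, 60 per arm, 11 independent tests, no baseline adjustment:

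| True effects | FDR | Per-test power |
|---|---|---|
| 5 | 5.4% | 73% |
| 4 | 6.3% | 70% |
| 3 | 7.3% | 66% |
| 2 | 8.2% | 62% |
| 1 | 9.1% | 56% |

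With none true the FDR is 10%, within simulation error. Power is below 82% (fixed 0.074) because the thresholds adapt: with 4 or 5 declarations among 11 they are 4 × 0.10 / 11 = 0.036 and 5 × 0.10 / 11 = 0.045.

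**4. Baseline adjustment.** ANCOVA with baseline correlation r multiplies the residual SD by √(1 − r²). At alpha 0.074 and 80% power the t-test detects 0.483 SD. ANCOVA detects 0.473 at r = 0.2, 0.418 at r = 0.5 (0.483 × 0.866) and 0.345 at r = 0.7. Under Benjamini-Hochberg, allowing 4 extra degrees of freedom for baseline and three stratum terms, power with 5 true and with 1 true is 76% and 58% at r = 0.2, and 87% and 71% at r = 0.5. With 5 of 11 true, r of about 0.35 is needed to regain 80%. The SAP gives no value of r. No precision gain from the strata themselves was calculated.

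**The case against.** The strongest reply is that 0.074 sits inside a power statement and nothing says a cytokine will be declared at p < 0.074. This stands. A reader might infer that the plan commits to that threshold and so runs an FDR of up to about 35%, or that 0.074 is miscalculated. The SAP supports neither: the arithmetic is right, and the inflation figures describe a possible misuse. What remains is that no other rule is given.

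The count of 11 is back-solved, and the panel size may be in the protocol, which is not at hand. This also stands, so the percentages are illustrations and the inferred 6 nulls should not be written into the SAP as the sponsor's own.

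An unadjusted t-test is valid in a randomised comparison, and the SAP plans longitudinal models for cytokine change and covariate adjustment in supportive analyses. It would therefore be wrong to conclude that the cytokine data are analysed only by unadjusted tests, or that the t-tests are biased. But those other analyses carry no FDR control, and the listed covariates do not name baseline cytokine level. The adjustment point is limited to the t-tests, and its gain is small if the baseline correlation is low.

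Finally, the tests are labelled preliminary, and the section ends by calling for independent validation. That closing remark follows the discussion of prediction models, whereas cytokine change by arm is a secondary objective in Section 12.1. The preliminary label still lowers the stakes.

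**Conclusion.** The point holds in limited form. Section 12.4 attaches a 10% FDR to the cytokine t-tests without a rule that achieves it on observed p-values, and those tests omit the collected baseline level and the strata. The planning figure is correct. It would fail as a cut-off once fewer cytokines differ than planned, already at 4 instead of 5 true effects under the assumption of 11 independent tests at 80% power. The size of any excess depends on the unstated number of tests, the number of true effects and the correlation between cytokines. The gain from ANCOVA depends on the unknown baseline correlation. Severity is low: no primary conclusion rests on these tests.

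**What to change.** In the Cytokine Analysis part of SAP Section 12.4:

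1. Replace the two-sample t-tests with ANCOVA of the (transformed) follow-up cytokine level at a named visit on treatment, baseline level and randomisation strata.
2. Declare individual cytokines by Benjamini-Hochberg at q = 0.10 over a stated family, giving the number of cytokines and visits in it.
3. Label 0.074 as a planning value, and have the sponsor state the number of tests behind it.
4. State that 80% power per test holds only under the planning assumptions.
5. Keep the longitudinal models for cytokine change over time.

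This is a change of wording and needs no new data. The cost is power: fewer cytokines will be declared when few truly differ, and the stated 80% is not met under Benjamini-Hochberg unless baseline adjustment makes up the loss. If cytokines are correlated at 0.5, power before adjustment is slightly lower again, about 71% with 5 true and 54% with 1.
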